9.7.8 Safety Variables

Safety in this study will be determined from evaluation of AEs, clinical laboratory assessments with a particular attention to the liver function, vital signs assessments, physical examinations, and immunogenicity. In case of a safety concern, additional unscheduled laboratory tests may be performed locally (at the Investigator's discretion) in order to facilitate timely and appropriate clinical management decisions; where possible, a matched sample for testing at the central laboratory should be collected (using the Unscheduled Visit lab kit) at the same time as the local unscheduled sample

9.7.8.1 Adverse Events

The determination, evaluation and reporting of AEs will be performed as outlined in Section 10.

9.7.8.2 Clinical Laboratory Assessments

The scheduled clinical laboratory tests are listed in [Table 9.7.8.2.1](#). Refer to the On Site File Binder for instructions on obtaining and shipping samples.

Any abnormal test results determined to be clinically significant by the Investigator should be repeated (at the Investigator's discretion) until: (1) the cause of the abnormality is determined; (2) the value returns to baseline or to within normal limits; or (3) the Investigator determines that the abnormal value is no longer clinically significant.

All abnormal clinical laboratory results should be initialed and dated by an Investigator, along with a comment regarding whether or not the result is clinically significant. Each clinically significant laboratory result should be recorded as an adverse event.

The diagnosis, if known, associated with abnormalities in clinical laboratory tests that are considered clinically significant by the Investigator will be recorded on the AE eCRF.

In case of a safety concern, additional unscheduled laboratory tests may be performed locally (at the Investigator's discretion) in order to facilitate timely and appropriate clinical management decisions; where possible, a matched sample for testing at the central laboratory should be collected (using the Unscheduled Visit lab kit) at the same time as the local unscheduled sample.

Table 9.7.8.2.1: Clinical Laboratory Tests

Blood Chemistry	Hematology	Urine Tests	Coagulation Screen including:
Albumin	Hemoglobin	Appearance	APTT
BUN	Hematocrit	Color	PT/INR
Calcium	WBC count	pH	TT
Chloride	RBC count	Specific gravity	
Total cholesterol	Platelet count	Ketones	
CPK	Differential cell count	Protein	
Creatinine	RBC indices (MCV and MCH)	Glucose	Other Tests:
CRP		Bilirubin	ABO blood typing*
Glucose		Nitrite	
Phosphorus		Urobilinogen	
Potassium		Hemoglobin	
Total protein			
Sodium			
Uric Acid			

BUN, blood urea nitrogen; CPK, creatinine phosphokinase; CRP, C-reactive protein; PT, prothrombin time; APTT, activated partial thromboplastin time; RBC, red blood cell; WBC, white blood cell; TT, thrombin time; INR, international normalized ratio; MCV, mean corpuscular volume; MCH, mean corpuscular hemoglobin.

*ABO blood typing assessment should be performed at Screening.

In addition to scheduled clinical laboratory assessments, a fasting blood lipid panel (including triglycerides, total cholesterol, HDL cholesterol, and LDL cholesterol) and

FibroTest will be assessed at the BMN 270 infusion visit. Subjects will fast for at least 8 hours prior to pre-infusion laboratory sampling on the day of the infusion visit.

In case of a Grade 2 or higher hypersensitivity or adverse drug reaction, a safety assessment including physical examination and vital signs will be performed and additional blood samples will be collected within 1 hour, and 8-24 hours following the hypersensitivity reaction for assessment of complement (C3, C3a, C4, Bb, and sC5b-9) and tryptase.

Additional samples will be collected at the 1 hour and 8-24 hour time points and, if possible, 1 week after the event for an optional, exploratory CBA to assess inflammatory biomarkers and plasma cytokine levels. Inpatient observation can be extended and additional blood samples can be collected if deemed necessary at the discretion of the Investigator and Medical Monitor.

At applicable sites, certain study assessments may be performed by an MN professional at the patient's home or another suitable location, such as their school or office, to improve access and convenience for patients participating in the study. The Sponsor may select a healthcare company that will be responsible for providing MN services for participating sites (the MN vendor). The MN vendor is responsible for ensuring that all MN professionals are licensed, qualified, and in good standing, as per applicable regulations, and that appropriate background checks have been performed. If the investigator at a participating site determines that MN services are appropriate for a patient and the patient gives written informed consent to participate in MN visits, the MN network will communicate with the patient and the patient's site. MN visits will be allowed at the visits indicated in the Schedules of Events. Unscheduled visits may also be conducted by MN as appropriate.

9.7.8.3 Liver and Hepatitis Testing

Subjects will be screened for evidence of previous or active hepatitis B or hepatitis C infection at Screening; hepatitis B screening should include HBsAg, HBsAb, and HBcAb. Subjects with documented results showing an absence of active hepatitis B or hepatitis C infection (as measured by negative surface antigen or DNA for hepatitis B or negative RNA testing for hepatitis C) 30 days prior to providing signed informed consent do not need to repeat those tests during the screening period.

Evidence of ongoing hepatitis B or hepatitis C infection is exclusionary. Subjects with a history of hepatitis B or hepatitis C infection prior to study entry will be tested for hepatitis B and hepatitis C reactivation at the timepoints listed in [Table 9.1.6](#). Subjects with a history of

hepatitis B or hepatitis C will be asked for information about the treatments received as part of their medical history assessment at Screening.

A liver ultrasound/FibroScan and liver tests (LTs) during Screening will identify any significant hepatic dysfunction.

LTs will be monitored on a regular basis; at each time point, the following LTs should be assessed:

Table 9.7.8.3.1: Liver Tests

Liver Tests (LTs)			
Alkaline Phosphatase	AST (SGOT)	Total Bilirubin	LDH
ALT (SGPT)	Direct Bilirubin	GGT	

ALT, alanine aminotransferase; AST, aspartate aminotransferase; GGT, gamma-glutamyltransferase; LDH, lactate dehydrogenase; SGOT, serum glutamic-oxaloacetic transaminase; SGPT, serum glutamic-pyruvic transaminase

Elevated ALT levels (above the upper limit of normal range) should be evaluated according to the following plan:

Table 9.7.8.3.2: Evaluation of ALT Elevations

ALT Level	Work-Up
≥1.5x Baseline - <2x Baseline	
 Continue to monitor LTs and FVIII per protocol (repeat within 24-72 hours if next protocol scheduled visit is >24-72 hours from the time of the reported ALT elevation) Consider evaluation to rule out alternative etiology (eg, concomitant medications, viral or autoimmune hepatitis, alcohol use, recreational drug use, special diets, strenuous exercise, prior and/or concurrent illnesses, exposure to environmental and/or industrial chemicals, etc.) (refer to Table 9.7.8.3.3.) If ALT is > ULN or > 2x baseline in 2 consecutive assessments within 24-72 hours and alternative etiologies have been ruled out, start oral corticosteroids upon consultation with the Medical Monitor (refer to Section 9.4.8.2) Consider liver biopsy at the discretion of the Investigator or Medical Monitor
≥2x Baseline or > ULN - <3x ULN	
 Repeat LTs and FVIII within 24-72 hours Continue to monitor LTs weekly until ALT is stable or improving Evaluate and rule out alternative etiologies (as above) Consult with Medical Monitor If ALT is ≥ 2x baseline or > ULN - <3x ULN in 2 consecutive assessments within 72 hours and alternative etiologies have been ruled out, start oral corticosteroids upon consultation with the Medical Monitor (refer to Section 9.4.8.2) Obtain other possibly relevant laboratory evaluations (albumin, PT/INR, CRP, etc.) Obtain complete blood count with differential to assess for eosinophilia Obtain PBMC to evaluate potential immune response (prior to starting oral corticosteroids) If no improvement in 14 days, consider gastroenterology and/or hepatology consult, abdominal workup, imaging (including MRI or ultrasound), and/or liver biopsy as appropriate
≥3x ULN	
 Consult with Medical Monitor Evaluate and rule out alternative etiologies (as above) Repeat LTs and FVIII within 24-48 hours, and continue with monitoring of LTs at least twice weekly for as long as the subject's ALT remains ≥ 3x ULN If ≥3x ULN in 2 consecutive assessments within 48 hours, start oral corticosteroids (refer to Section 9.4.8.2) Obtain other possibly relevant laboratory evaluations (albumin, PT/INR, CRP, etc.) Obtain complete blood count with differential to assess for eosinophilia Obtain PBMC to evaluate potential immune response (prior to starting oral corticosteroids) If no improvement in 14 days, consider gastroenterology and/or hepatology consult, abdominal workup, imaging (including MRI or ultrasound), and/or liver biopsy as appropriate

When ruling out alternative viral or autoimmune hepatitis as part of the elevated ALT workup, the following tests should be performed:

Table 9.7.8.3.3: Viral and Autoimmune Hepatitis Testing

Viral Hepatitis Workup Testing	Autoimmune Hepatitis Workup Testing
Hepatitis A	Smooth muscle antibody
Hepatitis B	Mitochondrial antibody
Hepatitis C	Liver/kidney microsomal antibodies
Hepatitis E	Antinuclear antibody (ANA) HEP-2
Cytomegalovirus (CMV)	
Epstein-Barr virus (EBV)	
Herpes simplex virus (HSV) 1 & 2	

9.7.8.4 HIV Testing

HIV testing will be performed at Screening. Subjects with documented negative results within the last 30 days prior to screening do not need to be retested.

9.7.8.5 Vital Signs, Physical Examinations and Other Observations Related to Safety

Vital signs will include seated systolic and diastolic blood pressure, heart rate, respiration rate, and temperature. Any clinically significant change in vital signs will be recorded as an AE.

Systolic blood pressure, diastolic blood pressure, heart rate, respiration rate, and temperature will be assessed at the timepoints indicated in the schedules of events. On the day of the BMN 270 Infusion, vital signs will be monitored prior to infusion, during the infusion every 15 minutes (\pm 5 minutes), following the infusion hourly (\pm 5 minutes) for at least 8 hours during the subject's stay in the clinic. Any abnormal vital sign assessments should be repeated, and both values should be recorded in the eCRF.

A complete physical examination should be performed during Screening/Baseline, at Week 26 (\pm 2 weeks) and 52 and every 52 weeks thereafter; at other visits, brief physical examinations may be performed at the discretion of the Investigator based on the subject's clinical condition. Particular attention should be given to signs of bleeding, as well as assessing possible hemarthroses.

A complete physical examination will include general appearance (head, eyes, ears, nose, and throat), cardiovascular, dermatologic, lymphatic, respiratory, gastrointestinal, genitourinary, musculoskeletal, and neurologic systems.

A brief physical examination will include general appearance, cardiovascular, dermatologic, respiratory, gastrointestinal, musculoskeletal, and neurologic assessments.

Height will be recorded at Screening only. Weight will be recorded at Screening and then at the timepoints indicated in the Schedules of Assessments.

9.7.8.6 Vector Shedding

During the Post-Infusion Follow-Up period, subjects will undergo testing of various bodily samples to look for evidence of vector shedding for possible viral transmission. Bodily fluids will be tested by polymerase chain reaction (PCR). Fluids tested will include:

- Blood
- Saliva
- Semen
- Urine
- Stool

Vector shedding will also be extensively studied in the present clinical trial. Testing will continue until at least 3 consecutive results below the limit of detection are obtained; additional collection and testing may be performed based on batch testing schedules, result turnaround times, or discussions between Medical Monitor and Investigator. Testing of semen will continue at least through Week 12, even if 3 consecutive results below the limit of detection have been recorded in that compartment prior to that time point. Subjects who have not had 3 consecutive semen samples below the limit of detection by Week 52 should continue to have PCR testing in semen every 4 weeks (during Year 2) or every 6 weeks (during Years 3-5) until 3 consecutive samples below the limit of detection are documented (or upon consultation between the Investigator and Medical Monitor).

Samples may be fractionated prior to shedding analysis in order to better characterize the presence, structure, and location of vector DNA and/or vector capsid within each matrix. If needed, the fractionation may be performed with samples collected specifically for shedding analysis (saliva, blood, semen, urine, stool). Alternatively, the vector DNA characterization during shedding analysis may utilize already fractionated exploratory samples obtained from the above biofluids, such as exploratory plasma samples, exploratory PBMC samples, and red blood cells recovered during PBMC/plasma isolations.

Fractionation of semen to collect purified sperm separately from non-sperm cells may be performed, after consultation between the Medical Monitor and the Investigator, in parallel at any visit where semen samples are collected. The shedding analysis of a fractionated semen

sample will only be performed if vector DNA was detected in the whole semen sample for the same visit. Fractionation of semen during shedding analysis may be stopped if purified sperm tested positive for vector DNA on at least three visits, or if purified sperm tested below the limit of detection for vector DNA on at least three consecutive visits.

Contraception use may need to be extended beyond 12 weeks in individual subjects based on observed vector shedding in semen. After 12 weeks, subjects may stop contraception use only if they have had 3 consecutive semen samples below the limit of detection (upon consultation between the Investigator and Medical Monitor).

Details for sample collection and storage are provided in the Laboratory Manual.

10 REPORTING ADVERSE EVENTS

10.1 Safety Parameters and Definitions

Safety assessments will consist of monitoring and recording protocol-defined AEs and SAEs; measurement of protocol-specified hematology, clinical chemistry, and urinalysis variables; measurement of protocol-specified vital signs; and other protocol-defined events of special interest that are deemed critical to the safety evaluation of the study drug.

10.1.1 Adverse Events

For this protocol, an adverse event (AE) is any untoward medical occurrence in a subject, temporally associated with the use of study intervention, whether or not considered related to the study intervention.

An AE can therefore be any unfavorable and unintended sign (including an abnormal laboratory finding), symptom, or disease (new or exacerbated) temporally associated with the use of study intervention.

Events meeting the AE definition include:

- Exacerbation of a chronic or intermittent pre-existing condition including either an increase in frequency and/or intensity of the condition.
- New conditions detected or diagnosed after study intervention administration even though it may have been present before the start of the study.
- Signs, symptoms, or the clinical sequelae of a suspected drug-drug interaction.

Events not meeting the AE definition include:

- Any clinically significant abnormal laboratory findings or other abnormal safety assessments which are associated with the underlying disease, unless judged by the investigator to be more severe than expected for the subject's condition.
- The disease/disorder being studied or expected progression, signs, or symptoms of the disease/disorder being studied, unless more severe than expected for the subject's condition.
- Medical or surgical procedure (eg, endoscopy, appendectomy): the condition that leads to the procedure is the AE.
- Situations in which an untoward medical occurrence did not occur (social and/or convenience admission to a hospital).
- Anticipated day-to-day fluctuations of pre-existing disease(s) or condition(s) present or detected at the start of the study that do not worsen.

10.1.1.1 Bleeding and Suspected Bleeding Events

All bleeding events and suspected bleeding events, regardless of the need for exogenous FVIII therapy as treatment, should be captured in subject diaries and recorded on the designated bleeding eCRF. Bleeding events and suspected bleeding events should not be reported as adverse events, with the following exception:

- All bleeding events and suspected bleeding events which meet one or more of the criteria for being serious (refer to Section 10.2) should be reported as serious adverse events (whether or not they are bleeding events that are normal sequelae of hemophilia, and whether or not they required exogenous FVIII as treatment).

10.2 Serious Adverse Events

A serious adverse event (SAE) is any untoward medical occurrence that, at any dose:

- Results in death
- Is life-threatening

Note: Life-threatening refers to an event in which the subject was at risk of death at the time of the event. It does not refer to an event, which hypothetically might have caused death, if it were more severe.

- Requires inpatient hospitalization or prolongation of existing hospitalization

Note: In general, hospitalization signifies that the subject has been detained (usually involving at least an overnight stay) at the hospital or emergency ward for observation and/or treatment that would not have been appropriate in the physician's office or outpatient setting. If the investigational product preparation, infusion, and post-infusion observation period require transfer to an inpatient setting for completion, in the absence of an AE, this will not be considered an SAE.

Complications that occur during hospitalization are AEs. If a complication prolongs hospitalization, the event is serious.

Hospitalization for elective treatment of a pre-existing condition that did not worsen from baseline is not considered an AE.

- Results in persistent or significant disability or incapacity
- Is a congenital anomaly or birth defect in the child or fetus of a subject exposed to IP prior to conception or during pregnancy
- Is an important medical event or reaction – that, based on medical judgment, may jeopardize the subject or require medical/surgical intervention to prevent one of the other outcomes listed above (eg, anaphylaxis)

10.2.1 Events of Special Interest (EOSI)

The following EOSI need to be reported to the Sponsor within 24 hours of site awareness, irrespective of seriousness, severity or causality:

- Elevation of ALT > ULN or > 1.5x baseline value, regardless of whether that elevation triggers an initiation or modification of oral corticosteroid treatment
- Thromboembolic event
- Immediate reactions: infusion-related reactions, hypersensitivity adverse events, or anaphylaxis
- Development of anti-FVIII inhibitory antibodies (inhibitors)

10.3 Methods and Timing for Capturing and Assessing Safety Parameters

10.3.1 Adverse Event Reporting Period

The study AE reporting period is as follows:

- After informed consent but prior to initiation of study drug, only SAEs associated with any protocol-imposed interventions will be collected. AEs occurring during this time period should be recorded on the Medical History eCRF.
- After informed consent is obtained and following infusion of study drug, the reporting period for all non-serious AEs and SAEs begins and continues for approximately 5 years or until study discontinuation/termination, whichever is longer.

The criteria for determining, and the reporting of SAEs is provided in Section 10.2.

10.3.2 Eliciting Adverse Events

Care will be taken not to introduce bias when detecting AEs and/or SAEs. Open-ended and non-leading verbal questioning of the subject is the preferred method to inquire about AE occurrences. The Investigator will record all relevant AE/SAE/EOSI information in the subject's medical record and AE Case Report Form (eCRF).

10.3.3 Assessment of Seriousness, Severity, and Causality

The Investigator responsible for the care of the subject or medically qualified designee will assess AEs for severity, relationship to study drug, and seriousness (refer to Section 10.2 for SAE definitions). These assessments must be made by a study clinician with the training and authority to make a diagnosis (eg, MD/DO, physician's assistant, nurse practitioner, or DDS).

10.3.3.1 Seriousness

The Investigator will assess if an AE should be classified as “serious” based on the seriousness criteria enumerated in Section 10.2. Seriousness serves as a guide for defining regulatory reporting obligations.

10.3.3.2 Severity

Severity (as in mild, moderate, or severe headache) is not equivalent to seriousness, which is based on subject/event outcome or action criteria usually associated with events that pose a threat to a subject’s life or functioning. The Investigator will determine the severity of each AE, SAE and EOSI using the Common Terminology Criteria for Adverse Events (NCI CTCAE) v5. Adverse events that do not have a corresponding CTCAE term will be assessed according to the general guidelines for grading used in the CTCAE v5 as stated in Table 10.3.3.2.1

Table 10.3.3.2.1: Adverse Event Grading (Severity) Scale

Grade	Description	
1	Mild: asymptomatic or mild symptoms; clinical or diagnostic observations only; intervention not indicated	
2	Moderate: minimal, local or noninvasive intervention indicated; limiting age-appropriate instrumental activities of daily living (ADL) ^a	
3	Severe or medically significant but not immediately life-threatening: hospitalization or prolongation of hospitalization indicated; disabling; limiting self-care ADL ^b	
4	Life threatening consequences; urgent intervention indicated	Grade 4 and 5 AEs should always be reported as SAEs
5	Death related to AE	

^a Instrumental ADL refer to the following examples: preparing meals, shopping for groceries or clothes, using the telephone, managing money.

^b Self-care ADL refer to the following examples: bathing, dressing and undressing, feeding oneself, using the toilet, taking medications, not bedridden.

10.3.3.3 Causality

The Investigator will determine the relationship of an AE to the study drug and/or corticosteroids and/or other immunosuppressant agents and will record it on the source documents and AE eCRF. To ensure consistency of causality assessments, Investigators should apply the guidance in [Table 10.3.3.1](#).

Table 10.3.3.3.1: Causality Attribution Guidance

Relationship	Description
Not Related	
 • Exposure to the IP and/or corticosteroids has not occurred OR • The administration of the IP and/or corticosteroids and the occurrence of the AE are not reasonably related in time OR • The AE is considered likely to be related to an etiology other than the use of the IP and/or corticosteroids; that is, there are no facts, evidence, or arguments to suggest a causal relationship to the IP and/or corticosteroids.
Related	
 • The administration of the IP and/or corticosteroids and the occurrence of the AE are reasonably related in time AND • The AE could possibly be explained by factors or causes other than exposure to the IP and/or corticosteroids OR
	
 • The administration of IP and/or corticosteroids and the occurrence of the AE are reasonably related in time AND • The AE is more likely explained by exposure to the IP and/or corticosteroids than by other factors or causes.

Factors suggestive of a causal relationship could include (but are not limited to):

- Plausible temporal relationship
- Absence of alternative explanations
- Rarity of event in a given patient or disease state
- Absence of event prior to study drug and/or corticosteroid exposure
- Consistency with study product pharmacology
- Known relationship to underlying mechanism of study drug and/or corticosteroid action
- Similarity to adverse reactions seen with related drug products
- Abatement of AE with discontinuation of study drug and/or corticosteroids, and/or recurrence of AE with reintroduction of study drug and/or corticosteroids

The Investigator's assessment of causality for individual AE reports is part of the study documentation process. Regardless of the Investigator's assessment of causality for individual AE reports, the Sponsor will promptly evaluate all reported SAEs against

cumulative product experience to identify and expeditiously communicate possible new safety findings to Investigators and applicable regulatory authorities.

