
 • Change from baseline in the annualized utilization (IU/kg/year) of exogenous FVIII replacement therapy during Weeks 5-52 post-BMN 270 infusion, for subjects receiving FVIII prophylaxis during the 12 months prior to study entry, or change from baseline in the annualized utilization (mg/kg/year) of emicizumab during Week 27 to Week 52 post-BMN 270 infusion for subjects receiving prior emicizumab prophylaxis • Change from baseline in the annualized infusion rate (number/year) of exogenous FVIII replacement therapy during Weeks 5-52 post-BMN 270 infusion, for subjects receiving FVIII prophylaxis during the 12 months prior to study entry, or change from baseline in the annualized utilization (mg/kg/year) of emicizumab during Week 27 to Week 52 post-BMN 270 infusion for subjects receiving prior emicizumab prophylaxis • Change from baseline in the annualized number of bleeding episodes (number/year) requiring exogenous FVIII replacement treatment during Weeks 5-52 post-BMN 270 infusion for subjects receiving prior FVIII prophylaxis, or Weeks 27-52 post-BMN 270 infusion for subjects receiving prior emicizumab prophylaxis from baseline 		

Mean change from baseline and associated 95% confidence interval will be calculated for the total score of Haemo-QoL-A at Week 52 post-BMN 270 infusion as well.
		

The incidence of AEs will be summarized by system organ class, preferred term, relationship to study drug, seriousness, and severity. Clinical laboratory test values, vital signs, vector shedding and immune response parameters will be summarized descriptively by visit.
		

The final analysis for the study will be performed after all subjects have been followed for 52 weeks post-BMN 270 infusion (or have discontinued study participation prior to Week 52). No formal interim analysis is planned. Informal analyses (ie, no hypothesis testing) may be performed at different timepoints to assess efficacy and safety over time. The primary efficacy endpoint for such analyses involves hFVIII activity, as measured by chromogenic substrate assay, and is defined as median FVIII activity during a specific 4-week time interval post-BMN 270 infusion.
		

Details of the planned analyses will be specified in the SAP.
		

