9.3.3.1 Study Safety Evaluation Criteria

If any of the following events occur in a subject in the study who has received BMN 270 infusion, an urgent evaluation by the DMC will be required and further enrollment into the trial will be temporarily put on hold if recommended by the DMC per Section 9.1.

1. Liver dysfunction (criteria do not apply to ALT elevations with an extra-hepatic etiology):
 - ALT > 5x ULN, for more than 2 weeks
 - ALT > 3x ULN **and** (total bilirubin > 2x ULN **or** INR >1.5)
 - ALT > 3x ULN with signs and symptoms of liver dysfunction
2. The occurrence of Grade 4 or Grade 5 adverse events assessed as related to study drug (events of liver dysfunction are defined above).
3. The occurrence of an AE of hepatic failure.
4. The detection of high-titer neutralizing antibodies (>5 BU) to hFVIII following BMN 270 infusion in two subjects.
5. The occurrence of any cancer (except non-melanoma skin cancer) at any point after BMN 270 infusion.
6. The occurrence of a thromboembolic event with FVIII activity > 150 IU/dL in one subject.

If any of the following events occurs in a subject in the study who has received BMN 270 infusion, an urgent evaluation by the DMC will be required. Further enrollment into the trial will continue while DMC evaluation is ongoing, unless deemed otherwise by the DMC:

1. The detection of high-titer neutralizing antibodies (>5 BU) to hFVIII following BMN 270 infusion in one subject.
2. Occurrence of a thromboembolic event in one subject.

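### The causality table's first 'Related' branch asks whether another cause is possible, not whether the exposure is, and its criteria pool BMN 270 with corticosteroids

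*Protocol*

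**What the plan says.** Protocol Section 10.3.3.3 has the investigator judge each adverse event against the study drug, corticosteroids and other immunosuppressants, joined by and/or. It offers Table 10.3.3.3.1 so that these judgements are consistent.

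- **Related, first branch:** exposure and event must be plausibly close in time, with this second condition: "The AE could possibly be explained by factors or causes other than exposure to the IP and/or corticosteroids". The branch suffices by itself.
- **Related, second branch:** the same timing condition, and "The AE is more likely explained by exposure to the IP and/or corticosteroids than by other factors or causes".
- **Not Related:** no exposure, or no reasonable relation in time, or a third criterion: "The AE is considered likely to be related to an etiology other than the use of the IP and/or corticosteroids". A gloss follows: "there are no facts, evidence, or arguments to suggest a causal relationship to the IP and/or corticosteroids".

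The list of suggestive factors below the table begins with plausible timing. No rule says which category prevails if both apply.

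Two places use the result. Section 9.3.3.1 requires an urgent evaluation by the data monitoring committee (DMC) on "The occurrence of Grade 4 or Grade 5 adverse events assessed as related to study drug". The Synopsis states, and Section 14.7 repeats: "The incidence of AEs will be summarized by system organ class, preferred term, relationship to study drug, seriousness, and severity". Both refer to study drug alone.

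**The concern.** The second condition of the first 'Related' branch points the wrong way. The possibility of another cause is normally a reason for doubt about a causal link. Here, once timing is satisfied, it is what makes the event 'Related'. The third 'Not Related' criterion also turns on another cause, so the two categories can compete for the same event.

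Pooling the agents adds to this. All subjects start corticosteroids on Day 1, before the infusion, on a 19-week regimen (Sections 9.1 and 9.4.8.2), so both exposures coincide in everyone. Section 7.4 says that the effect of adding prophylactic corticosteroids still needs study. The guidance should therefore help investigators to tell the two agents apart, and its criteria do not.

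At stake are the consistency of causality coding between investigators, the meaning of the study-drug-related adverse event rate, and whether a given Grade 4 or 5 event activates one DMC trigger.

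**Working it through.** The protocol gives no figure to reproduce, so the check is logical. For a subject who has been exposed, describe an event by five yes/no attributes:

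- T: reasonably related in time
- O: another etiology is likely
- P: another cause is possible
- M: the exposure is the more likely explanation
- F: facts, evidence or arguments suggest a causal link

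Consistency rules (assumed): O implies P; O and M cannot both hold; M implies F; and a timed event with no other possible cause has M. These leave 8 untimed and 6 timed profiles, 14 in all.

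**Table rules.** Related = (T and P) or (T and M). Not Related = (not T) or criterion 3. Criterion 3 can be read in three ways:

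- **A:** O alone, ignoring the gloss.
- **B:** O and not F, where timing alone is not such a fact.
- **C:** O and not F, where timing is itself such a fact, so T implies F.

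Untimed events are 'Not Related' on every reading. The six timed profiles are:

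| Timed event | F | Related? | Criterion 3, A | Criterion 3, B | Criterion 3, C |
|---|---|---|---|---|---|
| Other cause likely | no | yes, branch 1 | met | met | cannot occur |
| Other cause likely | yes | yes, branch 1 | met | not met | not met |
| Other cause possible, neither more likely | no | yes, branch 1 | not met | not met | cannot occur |
| Other cause possible, neither more likely | yes | yes, branch 1 | not met | not met | not met |
| Other cause possible, exposure more likely | yes | yes, both branches | not met | not met | not met |
| No other cause possible, exposure more likely | yes | yes, branch 2 | not met | not met | not met |

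**Results.**

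- Reading A: 2 of 14 profiles fall in both categories.
- Reading B: 1 of 14 does, the timed event with a likely other cause and no supporting facts.
- Reading C: two timed profiles cannot occur, leaving 14 − 2 = 12, and 0 of 12 fall in both. Criterion 3 then classifies no event that the timing criterion has not already classified, and every timed event with a likely other cause is 'Related'.

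Under these rules all 6 timed profiles are 'Related', because either another cause is possible (branch 1) or none is (branch 2). As written, 'Related' reduces to timing.

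**Pooling.** Every exposure condition in the table names the investigational product and/or corticosteroids. Take an event clearly caused by corticosteroids. Read jointly, it satisfies the second 'Related' branch although BMN 270 played no part. It cannot meet the third 'Not Related' criterion, because corticosteroids are not an etiology outside the named exposure. The lead sentence also names other immunosuppressants, but no table criterion covers them.

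**The case against.** The strongest reply is the gloss on the third 'Not Related' criterion. A likely other cause is not enough; nothing may point to the products. Since plausible timing heads the list of suggestive factors, a well-timed event has something pointing to the products and is simply 'Related'. This stands in part. It rules out the stronger reading a reader might infer, that any well-timed event with a likely other cause meets both categories. That holds in full only if the gloss is ignored. The reply does not rescue the table: the price is a redundant criterion and a 'Related' category decided by timing.

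Second, and/or can be read agent by agent, and Amendment 1 (summary item 6) adds an option to rate relatedness to other immunosuppressive agents, which suggests separate answers. This also stands. A reader might infer that the trial cannot separate BMN 270 events from corticosteroid events. The documents do not show that, because the case report form is not available. They show only that the criteria do not separate the agents.

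Third, safeguards limit the harm. Sites report all serious events and events of special interest within 24 hours regardless of relatedness (Section 10.5.1). Grade 4 and 5 events are always reported as serious (Table 10.3.3.2.1). The sponsor evaluates every serious event whatever the investigator's causality call (Section 10.3.3.3). The DMC reviews individual safety data throughout (Section 15), and its other triggers in Section 9.3.3.1 do not depend on relatedness. All of this stands, so an inference of missed events or missed site reporting is unsupported.

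Fourth, the table is original-protocol text. Amendment 1 lists it in its contents, but the available copy stops at Section 10.2.1. Its summary names no correction of this wording among the major changes, but item 15 covers unspecified minor clarifications. Whether the wording survives is therefore unknown.

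**Conclusion.** The point holds in limited form. The first 'Related' branch, as written on 28 February 2020, omits the question of whether the exposure could explain the event. The table therefore either overlaps with itself (1 or 2 of 14 profiles) or contains a redundant criterion (0 of 12 overlapping). These are counts of logical profiles, not of expected events, and they rest on the consistency rules stated above. The documents do not allow an estimate of how many events would be affected. With about 20 subjects, one recoded subject moves an incidence by 1/20 = 5 percentage points, but that is true of any yes/no item and does not measure this defect.

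The error runs towards calling events 'Related'. The likely consequences are inconsistent coding and over-attribution to BMN 270, which make the study-drug-related rate less informative and could activate the Grade 4/5 DMC trigger for events with another likely cause. No efficacy result is affected. The conclusion applies to current conduct only if Amendment 1 kept the wording.

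**What to change.** First check Table 10.3.3.3.1 in the current protocol version. If the wording persists:

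1. Keep the timing condition in the first 'Related' branch and replace the second condition, so that it asks whether exposure to the agent is a possible explanation, even though other causes are possible too.
2. State that 'Related' and 'Not Related' are mutually exclusive, and say whether timing alone counts as evidence under the third 'Not Related' criterion.
3. Apply the criteria separately to BMN 270, corticosteroids and other immunosuppressive agents, each time treating the remaining agents as other causes. The DMC trigger and the adverse event summary would then use the BMN 270 answer.

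The cost is revised table wording, a completion guideline for the case report form and a short memo to sites. If the form does not already hold a separate answer per agent, it would need those fields. Neither the design nor clinical management changes.
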